A Hybrid Type-I Implementation-effectiveness research design will allow the research team, comprising investigators with expertise in intervention development, efficacy and effectiveness research, and implementation science, to simultaneously investigate the effectiveness of *SAH-C* in a military population while identifying any barriers to implementation that would need to be addressed before *SAH-C* could be successfully implemented on a larger scale. The study site for this proposed effort is Joint Base Lewis McChord, Washington.

The primary hypotheses are that those receiving *SAH-C* will evidence greater reductions in physical and psychological IPV, and greater increases in relationship satisfaction, relative to those receiving *Supportive Prevention* across the follow up time points.

(c) Specific Objectives.

AIM 1: To test the effectiveness of *SAH-C* for military couples on an installation, we will conduct a randomized trial comparing 10 sessions of *SAH-C* to 10 sessions of *Supportive Prevention (SP)* under representative conditions, with 140 couples who are at risk for the development of IPA (risk is established if at least one member of the couple reports at or below a score of 100 on the Dyadic Adjustment Scale (DAS), a cutoff score used to distinguish relationship distress, or they report the presence of psychological aggression in the past three months). This aim will be fulfilled by accomplishing the following subaims:

Subaim 1.1: To compare the frequency of physical IPA perpetration of both members of the couple across conditions as reported by service members and their collateral relationship partners at post-intervention and two 3-month follow ups.

Subaim 1.2: To compare the frequency of psychological IPA perpetration of both members of the couple across conditions as reported by service members and their collateral relationship partners at post-intervention and two 3-month follow ups.

Subaim 1.3: To compare relationship satisfaction across conditions as reported by service members and their collateral relationship partners at post-intervention and two 3-month follow ups.

AIM 2: To explore differences in compliance factors across conditions, we will compare session attendance.

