We have recently examined the data from 78 returning male Veterans and their partners via Phase 2 of the CDC trial, with impressive results obtained. The mean incidents of Veteran and partner perpetrated psychological IPA, based on CTS2 and Multidimensional Measure of Emotional Abuse⁴⁵ reports, are presented in Table 1. Analyses of Covariance (ANCOVA) at 6 months post-intervention (controlling for baseline scores) revealed a significant effect of group whereby psychological IPA was significantly lower among *SAH-C* couples than *SP* couples, $F(1,46) = 6.37, p = .015$ (Figure 1). For partner perpetrated psychological IPA, an ANCOVA demonstrated a significant effect of group with *SAH-C* couples reporting a significant decrease in partner-perpetrated psychological IPA at 6 month follow-up compared to *SP* couples, $F(1,46) = 7.64, p = .008$ (Figure 2). MMEA results for Veteran and partner-perpetrated psychological IPA can be found in Figures 3 and 4, respectively. While based on the MMEA there was no difference in male Veteran-perpetrated psychological

IPA at 6-month follow-up for either the *SAH-C* or *SP* conditions, there was a trend-level reduction in partner-perpetrated IPA at the 6-month follow-up for *SAH-C* couples, $F(1,46)=3.822, p= .057$.

Table 1.

Reported IPA perpetration over time

Type of IPA	SAH Condition		ST Condition		Results of ANCOVA
	T1 (n=41) M(SD)	T3 (n=31) M(SD)	T1 (n=37) M(SD)	T3 (n=18) M(SD)	
Veteran-Perpetrated					
Psychological (CTS)	30.76 (25.9)	15.26 (17.0)	37.94 (26.7)	35.78 (25.9)	$F(1,46)=6.37, p=.015$
Psychological (MMEA)	66.98 (57.0)	41.48 (52.9)	95.46 (73.9)	76.28 (77.1)	$F(1,46)=1.46, p= .233$
Physical	.44 (2.5)	.74 (2.1)	.14 (.48)	.94 (2.1)	$F(1,46)=.378, p=.541$
Partner-Perpetrated					
Psychological (CTS)	30.29 (24.3)	11.94 (13.5)	32.84 (21.5)	32.40 (25.8)	$F(1,46)=7.64, p=.008$
Psychological (MMEA)	52.76 (38.9)	31.13 (34.1)	61.96 (67.3)	59.61 (67.8)	$F(1,46)=3.82, p= .057$
Physical	1.24 (3.4)	.51 (1.7)	.73 (1.7)	1.00 (2.1)	$F(1,46)=.971, p=.330$

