The PCL is widely used as an assessment for screening individuals for PTSD and monitoring change across time. This questionnaire includes a list of potential responses an individual may have following an extremely stressful experience⁸¹.

The AUDIT is a widely used screening tool to assess alcohol consumption and alcohol-related behaviors

The CTS-2 is the most widely used measure of IPA, with excellent internal consistency reliability, content validity, and construct validity.^{44,66} The measure assesses physical, psychological, and sexual aggression in intimate relationships. Respondents report on the frequency of each item for themselves and their partners. Combined partner reports are used to reduce IPA underreporting.

Because the CTS-2 assesses a fairly limited number of psychologically abusive behaviors, the Multidimensional Measure of Emotional Abuse (MMEA) will also be administered to assess psychological IPA.⁹⁶

The DAS is appropriate for use with both married and cohabitating couples. In addition to a global satisfaction score, this 32-item measure consists of four subscales: Dyadic Consensus, Affectional Expression, Dyadic Satisfaction, and Dyadic Cohesion. Several studies provide evidence for this measure's strong psychometric properties.⁶⁷⁻⁶⁹

The post-intervention satisfaction questionnaire asks questions to determine barriers and facilitators of the program. This information will be used to make adjustments to the program if necessary.

The partner contact form consists of a single item assessing the frequency of contact with the participant's partner.

In addition to the self-report questionnaires, a collateral contact form will be completed by each individual to ensure research staff will be able to contact the individual if they move away prior to the final time point. The form includes contact information for themselves as well as up to three others that research staff can contact if there is difficulty getting in contact with the participants.

Intervention and Integrity Measure Refinement

To facilitate the rapid integration of the information into the refinement of the intervention and materials, meeting summaries will be content analyzed using a rapid coding technique based on methods of Sobo et al.^{70,71}

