Participants may receive additional types of intervention during this trial. Any additional intervention will be monitored for descriptive purposes. Study participants may be terminated from the group if they become actively suicidal or homicidal or fail to attend three consecutive scheduled meetings without a reason deemed appropriate by their providers. All participants who are terminated early will continue to be followed for all subsequent assessments.

(f) Feasibility

In order to enhance recruitment and achieve our target recruitment goals, we will seek approval from the Medical Treatment Facility Commander and the Garrison Commander. We will then attend all hands meetings in order to brief the troops on this research. All necessary permissions from Medical and Line Commanders will be obtained in order to accomplish this research. Preliminary conversations have already commenced with these officers, who have expressed their willingness to meet with us to find the best way to implement the study once the grant has been awarded.

There are currently 383 referrals annually to the Family Advocacy Program at Madigan Army Medical Center that do not meet the criteria for domestic abuse, but still require help in working through the various challenges associated with solving differences about money, children, sex, and friends. In addition, there are 4 M&FTs who work full time providing services to couples who have not yet come to the attention of the Family Advocacy Program. These providers average around 210 couples per year each. Thus, there is a pool of more than 1,600 couples who could be referred for *SAH-C* during the recruitment period, which would help us easily meet our recruitment goal.

(g) Attrition

We expect relatively low attrition since we are only including participants if they indicate that they plan to remain on base for the next six months and given previous rates of attrition obtained by members of the study team. To limit attrition, the research coordinator will contact participants to schedule their in-person assessments. We have planned for a 12% attrition rate. Reasons for attrition will be assessed as potential barriers to implementation.

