Consistent with the REP process, findings will be presented to the Stakeholder Advisory Board at the end of the study, and will guide decisions regarding next steps for intervention refinement if needed, or for broader implementation. If, for example, findings indicate effectiveness of *SAH-C*, we will use findings regarding modifiable barriers and facilitator that can be leveraged to facilitate broader implementation and to guide the selection of appropriate implementation strategies and models for use in future research. In this case, a future study might be a Type-III Hybrid study, which would allow the testing of an implementation model for military settings. If, on the other hand, findings suggest that effectiveness is lower than in previous research, we will use qualitative findings to determine whether intervention-related contextual variables may have contributed to these findings, and determine appropriate next steps for research accordingly.

(g) Power Analysis

Power analyses were based on the main hypotheses that *SAH-C* would reduce the level of IPA to a greater degree than the *SP* condition by the 3-month follow-up assessments. Estimates affecting power (e.g., effect size, intra-class correlations, attrition) were derived from our prior CDC funded study.

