Our first consideration in estimating the necessary sample size for detecting differential change over time in *SAH-C* versus *SP* in terms of IPA incidence was the expected incidence rate of IPA during the follow-up period. Our sample is at high risk for such incidence as defined by the presence of high levels of marital distress. While there is no prospective military data available that directly speaks to such incidence rates, available estimates suggest a 33% one-year prevalence of IPA among trauma exposed service members.⁹³ Conservatively, it would be expected that during the current project, approximately 16% of cases of IPA would emerge (half of the one year prevalence). However, inclusion of only couples with high levels of marital distress will increase this estimated incidence rate. Accordingly, we expect an increase of 10% in the incidence rate. Together, we based power analyses on an estimated 26% one-year incidence rate. Our second consideration involved expected sample attrition. Based on our prior trial and the specific plan for data capture outlined for the project, we estimate that about 15% of participants will provide no follow-up assessment data. However, power analyses were conducted based on the conservative estimate of 20% assessment dropout. Consistent with an ITT approach, regardless of intervention dropout, we will assess participants randomized into the trial. Thus, dropout from measurement versus intervention is of greatest concern. Our third consideration involved expected within-subjects correlations. The within-subjects correlation was estimated as the average correlation observed in our previous trial for pre-intervention, post-intervention, and follow-up data on reports of physical and psychological IPA on the Revised Conflict Tactics Scale (CTS-2).⁴⁴ These correlations ranged from .53 to .90. We also considered the expected intra-class (group) correlation, which was approximately .05. Finally, consistent with recommendations,⁹⁴ we considered the intra-class (dyadic) correlation among couples. We did not incorporate an estimate of such correlations into power analyses because of our proposed use of a composite measure of IPA, which results in a single index of IPA, thereby eliminating intra-dyad correlations. Together, we assumed an intra-class correlation of .38 for power analyses. Our fifth consideration involved the expected effect size of the *SAH-C* relative to *ST*. Our prior work suggested an ITT effect size of $d = 1.01$. A conservative estimate of a mean effect size of $d = .5$ for the *SAH-C* in terms of reduction of IPA incidence was utilized for the power analysis.

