
Each of these considerations was used to calculate the needed sample size for testing the main hypotheses in the proposed project. Power analyses were conducted for the main hypothesis tests involving IPA perpetration and were conducted using the GEESIZE Macro in SAS Proc Mixed according to recommendations for estimating sample sizes needed in repeated measures experiments.⁹⁵ Together, assuming (1) 26% incidence of IPA in the control condition, (2) 20% overall attrition, (3) .70 within-subjects correlation, (6) $d = .5$, (5) two-tailed, and (6) $p < .05$, the proposed total N of 280 (140 couples) will provide ample power ($> .9$) to detect differences in IPA frequency across experimental conditions.

(8) Human Studies Section

(a) Risk to Subjects

Human Subjects Involvement and Characteristics

The study population consists of service members attached to an installation who may be at risk for intimate partner aggression (IPA) and their intimate partners. The participants will be 150 service members (10 in Phase 1; 140 in Phase 2) and their partners who will provide data on IPA. The research team has conducted several intervention studies with military samples. There are currently 383 referrals annually to the Family Advocacy Program at Madigan Army Medical Center that do not meet the criteria for domestic abuse, but still require help in working through the various challenges associated with solving differences about money, children, sex, and friends. In addition, there are 4 M&FTs who work full time providing services to couples who have not yet come to the attention of the Family Advocacy Program, Madigan Army Medical Center. These providers average around 210 couples per year each. Thus, there is a pool of more than 1,600 couples who could be referred for *SAH-C* during the recruitment period, which would help us easily meet our recruitment goal.

Inclusion/Exclusion Criteria

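### The 20% dropout behind the power statement is not shown to be conservative for six-month loss, the 12% attrition figure conflicts with it, and missing at random has no planned sensitivity analysis

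*Combined protocol and SAP*

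**What the plan says.** Section (7)(g), Power Analysis, states where its inputs come from: "Estimates affecting power (e.g., effect size, intra-class correlations, attrition) were derived from our prior CDC funded study". It then gives an expected loss, "we estimate that about 15% of participants will provide no follow-up assessment data", and a margin on top of it: "However, power analyses were conducted based on the conservative estimate of 20% assessment dropout". The closing list of assumptions in that section repeats the figure in other words: "2) 20% overall attrition, (3) .70 within-subjects correlation".

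Section (5)(g), Attrition, gives a third figure: "We have planned for a 12% attrition rate". It too appeals to attrition previously seen by the study team.

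The source trial is described under Preliminary Studies, SAH-C Randomized Clinical Trial: "We have recently examined the data from 78 returning male Veterans and their partners via Phase 2 of the CDC trial". Its Table 1 gives the number of couples by arm at T1 and at T3, and the text places the analysis six months after the intervention.

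Specific Objectives sets the assessments for the present trial "at post-intervention and two 3-month follow ups". Read as successive follow-ups, the last falls about six months after the intervention.

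Primary Data Analyses rests the random-effects model on data being missing at random. The Intent-to-Treat section relies on collecting complete data and expects losses to be small.

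**The concern.** A planning figure described as conservative should be at least as pessimistic as the evidence it comes from. Here the named source shows heavier loss than 20% at the visit that matches this trial's last visit, and the loss was much heavier in the control arm.

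Three percentages (12%, 15%, 20%) appear under four descriptions. A reader cannot tell whether the 20% means couples who give nothing after baseline or couples without a six-month outcome, so it is unclear what loss the stated power allows for.

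The second issue is inference. The outcome is partner aggression, and couples may stop reporting because of separation or conflict. If loss again differs by arm and depends on outcomes that were not observed, the estimated difference could move in either direction. Without a planned sensitivity analysis, nobody could say by how much.

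**Working it through.** **1. The plan's own power figure.** Inputs from the Power Analysis: total N 280 (140 couples), d = .5, two-sided .05, 20% attrition. On the simplest reading, 280 independent individuals in two equal arms, n per arm = 140 × (1 − .20) = 112. A two-sample comparison at d = .5 then has power of about .96, which agrees with the stated value above .9. Only the inequality can be checked. The protocol used GEESIZE and does not give every input, such as the number of time points or how the intra-class correlation of .38 enters.

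**2. Loss in the source trial, from Table 1.**

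| Arm | Couples at T1 | Couples at T3 (six months) | Without T3 data |
|---|---|---|---|
| SAH-C | 41 | 31 | 10/41 = 24.4% |
| Control | 37 | 18 | 19/37 = 51.4% |
| Both | 78 | 49 | 29/78 = 37.2% |

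The counts are internally consistent. 41 + 37 = 78 matches the text, and an ANCOVA with an intercept, a group term and a baseline covariate leaves 49 − 3 = 46 error degrees of freedom, as reported.

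- Overall loss: exact (Clopper-Pearson) 95% CI 26% to 49%, which lies wholly above 20%.
- Difference between arms: 51.4% − 24.4% = 27.0 points, Newcombe 95% CI 5 to 45, Fisher exact p = .019.
- Both arms' observed loss exceeds 20%. The SAH-C interval taken alone (12% to 40%) still includes 20%.

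**3. What each rate would mean for 140 couples.**

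- 12%: 140 × .12 = 17 couples lost
- 15%: 140 × .15 = 21
- 20%: 140 × .20 = 28
- 37.2%: 140 × 29/78 = 52
- By arm, 70 couples each: 70 × 10/41 = 17 and 70 × 19/37 = 36, together 53

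**4. How the percentages are defined.**

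| Figure | Where | What it describes |
|---|---|---|
| 12% | (5)(g) Attrition | attrition, not defined further |
| 15% | Power Analysis | no follow-up data at all |
| 20% | Power Analysis | assessment dropout |
| 20% | Power Analysis, list of assumptions | overall attrition |

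The 15% and the 20% are linked: the first is the expectation and the second adds a margin. The 12% is linked to neither. No text says whether the 20% covers loss at the last visit.

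**5. What is planned for missing data.** Three provisions come close to a check, and none is one:

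- The adequate-dose analysis concerns attendance.
- Reasons for attrition are collected under (5)(g), but as possible barriers to implementation.
- The Intent-to-Treat section aims for complete collection.

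None reports missingness by arm, and none examines outcomes that are not missing at random.

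**The case against.** The strongest reply is that 20% and 37% are different quantities. The 15% is loss from every follow-up, 20% adds a margin to it, and in that sequence conservative means conservative relative to 15%. The 37% is absence from one visit. This stands: Table 1 gives no T2 counts, so it cannot disprove the 15%. It also gives no reasons for absence, and data described as only recently examined may have been incomplete.

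Retention may also be better here. The Power Analysis relies on a new data-capture plan, (5)(e) keeps following participants whose group participation ends early, and a collateral contact form is meant to "ensure research staff will be able to contact the individual if they move away prior to the final time point". All of this is relevant, but the documents attach no figure to it that would bring six-month loss from 37% to 20%.

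A reader might infer that the trial is underpowered. The documents do not support that. The planned effect is intervention by time across the visits, in a model that keeps partial records. As a rough check, take a couple-level comparison of change to the mean of three follow-ups, with r = .70, d = .5 and group ICC .05. It keeps power of about .92 at 24% v 51% loss, even if couples without T3 data contribute no follow-up at all. That is not the protocol's GEESIZE calculation, so it neither confirms nor replaces the stated power.

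A reader might also infer that unequal loss by itself violates missing at random. It does not, because arm is in the model. Nor does the Intent-to-Treat section concede that the model is biased: its remark about bias concerns imputation approaches.

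Finally, part of the text is unavailable, and the visible analysis subsections begin at (c). The absence of a sensitivity analysis is therefore a statement about the available text. The Intent-to-Treat and Primary Data Analyses sections, where such an analysis would be expected, are present and contain none.

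**Conclusion.** The concern holds in a limited form. The only source-trial counts in the protocol show six-month loss of 37% (26% to 49%), and 24% v 51% by arm. The visible text therefore does not justify calling 20% conservative for loss at the last visit. This rests on reading Table 1's T3 counts as couples with six-month data, and the two follow-ups here as ending about six months after the intervention. The 12% is undefined and conflicts with the 15% and 20%. The primary analysis depends on missing at random with no visible plan to test how sensitive the result is to it, although loss in the team's own trial differed by 27 points between arms. Whether that imbalance will recur, and in which direction any bias would run, cannot be known from the documents. The point deserves correction but does not invalidate the design.

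**What to change.** 1. In (5)(g) and (7)(g), define the 20% either as no follow-up assessment at any visit or as no six-month outcome. Replace the 12% or reconcile it with that definition. Remove the word conservative, or justify it against Table 1 by arm.
2. Rerun the protocol's own power calculation, with the same GEESIZE method and correlations, at 37% and at 24% v 51% six-month loss. State the results beside the 20% figure. Do not enlarge the sample on this account.
3. Add to Primary Data Analyses: *Missingness and its reasons will be reported by arm and visit. As a prespecified sensitivity analysis, missing outcomes will be multiply imputed under missing at random, and the imputed values will then be shifted separately in each arm until the conclusion changes (tipping point).*

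The cost is some wording, a rerun of the power calculation at two further loss scenarios and one additional analysis, with no new data collection. The stated power may become less favourable.

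### The single power figure of > .9 for 280 participants (140 couples) is not supported as written: the analysis unit is inconsistent, and no separate power is given for physical IPA

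*Combined protocol and SAP*

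**What the plan says.** All of this is in (g) Power Analysis unless another section is named.

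- **Unit.** Dyadic correlation was considered but not incorporated, because of "our proposed use of a composite measure of IPA, which results in a single index of IPA, thereby eliminating intra-dyad correlations". The closing statement is that "the proposed total N of 280 (140 couples) will provide ample power", with the figure > .9.
- **Intra-class correlation.** The section reports an "expected intra-class (group) correlation, which was approximately .05". After setting the dyadic correlation aside it says: "Together, we assumed an intra-class correlation of .38 for power analyses". No level is given for the .38.
- **Incidence.** The starting point is a 33% one-year prevalence. Half of it, about 16%, is expected during the project, and 10 points are added for marital distress. The result is then labelled: "Together, we based power analyses on an estimated 26% one-year incidence rate".
- **Effect size.** d = .5 "in terms of reduction of IPA incidence was utilized for the power analysis", but the power is claimed "to detect differences in IPA frequency across experimental conditions".
- **Outcomes.** Section (1)(b) and Subaims 1.1 and 1.2 name physical and psychological IPA separately, for both members of the couple. The Inclusion/Exclusion Criteria require both partners to report no physical IPA in the past 3 months. (d) Primary Data Analyses makes the intervention-by-time interaction the primary effect.

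**The concern.** Neither reading of the composite gives 280 units with no dyadic correlation. One index per couple gives 140 units. One two-reporter index per perpetrator fits the subaims and gives 280 scores, but the two scores from one couple are still correlated. If 280 is only a headcount, the section does not say that the calculation used 140.

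The second problem is that one figure serves two different outcomes. Psychological IPA is present at baseline in many couples, so a within-subject correlation of .70 sharpens the comparison. Physical IPA is absent at entry by design, so recent baseline scores have no variation for that correlation to use.

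A reader will take > .9 as applying to physical IPA, which is a primary hypothesis. Section (11) says the prior trial prevented physical IPV, while the account of that trial under (3)(a) reports no significant group effect on it. A null physical result could then be read as lower effectiveness than before and start the search for contextual causes described in (f), although power for that outcome was never stated.

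**Working it through.** **Inputs from the plan:** two-sided .05; d = .5; 20% loss; r = .70; group ICC .05; 14 groups per arm with 5 couples each; 26% incidence in controls.

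**Assumptions made here:** equal arms; loss by whole couples, leaving 4 evaluable couples per group; equal correlation between all time points; 26% applied to couples, although its source is a prevalence among service members.

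**1. The plan's figure.** 280 × .8 / 2 = 112 per arm. A two-sample t test at d = .5 gives power .961. So > .9 is met with 280 people counted as independent, no ICC and one follow-up. Steps 2 and 3 show that other set-ups meet it too.

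**2. 140 couple composites.** 140 × .8 / 2 = 56 per arm. The group design effect is 1 + 3 × .05 = 1.15, so 56 / 1.15 = 48.7 effective couples per arm. The variance factor f depends on the contrast. Power is shown with group variance unaffected by the contrast (design effect f + .15) and with it reduced in proportion (1.15 f).

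| Contrast | f at r = .70 | Power, f + .15 | Power, 1.15 f |
|---|---|---|---|
| One follow-up, no baseline | 1 | .69 | .69 |
| Mean of three, no baseline | (1 + 2r)/3 = .80 | .77 | .78 |
| Change, one follow-up | 2(1 − r) = .60 | .86 | .89 |
| Baseline-adjusted, one follow-up | 1 − r² = .51 | .90 | .93 |
| Change to mean of three | 1 + .80 − 2r = .40 | .94 | .97 |
| Adjusted, mean of three | .80 − r² = .31 | .97 | .99 |

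The last four rows are closest to intervention by time: .86 to .99. The plan quotes correlations from .53 to .90. At r = .53, with a design effect of 1.20 (five couples per group), power is .70 for a single change score and .86 for change to the mean of three.

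**3. 280 perpetrator scores, taking .38 as the dyadic ICC.** There are 112 scores per arm and 8 per group. The design effect is f(1 + .38) + 6 × .05.

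- Change: .60 × 1.38 + .30 = 1.128, power .94.
- Adjusted: .51 × 1.38 + .30 = 1.004, power .96.
- Adjusted, mean of three: .31 × 1.38 + .30 = .728, power .99.
- No baseline: .82 at one follow-up, .88 for the mean of three.

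**4. New physical IPA, 140 couples.** This is a pooled two-proportion test with 48.7 per arm and no baseline gain. The plan does not give the scale of d, so three conversions from 26% are used. The averaged column divides 48.7 by .80, giving 60.9 per arm.

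| Reading of d = .5 | Intervention arm | Power, one outcome | Power, three averaged |
|---|---|---|---|
| Arcsine difference of .5 | 7.9% | .67 | .77 |
| Log odds ratio of .5π/√3 | 12.4% | .40 | .48 |
| Difference of .5 × √(.26 × .74) | 4.1% | .87 | .93 |

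In this test, .9 power needs 26% to fall to about 3.3% with one outcome, or about 5.1% with three averaged.

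**5. Is .5 conservative for physical IPA?** From Table 1 at T3 (n = 31 and 18):

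- Veteran: (.94 − .74) / 2.1 = .10.
- Partner: pooled SD √[(30 × 1.7² + 17 × 2.1²)/47] = 1.85, so (1.00 − .51) / 1.85 = .26.
- Standard error of each: about √(1/31 + 1/18) = .30.

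**The case against.** The strongest reply is that the plan's primary effect is the intervention-by-time interaction, so baseline enters, and most baseline variants with 140 couples reach about .9 or more. If .38 is the dyadic ICC, every baseline variant with 280 scores that was tried exceeds .9. The section also says that each of its considerations went into the calculation, so an ICC missing from the closing list of assumptions need not be missing from the run. All of this stands for psychological IPA. It does not settle the unit, because the same section says dyadic correlation was not incorporated, and it does not carry over to physical IPA.

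A second reply is that a two-proportion test is not the planned model, which is a random-effects regression on frequency over repeated assessments. That is fair. Averaging three assessments raises the physical figures, and on the most favourable scale of d they pass .9. The other two scales stay below.

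A reader might also draw three inferences that the documents do not support:

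- That the irregular numbering of the closing list shows an omitted input. It has six entries and six labels, so this is at most a slip.
- That the 26% should be cut again to a six-month rate. The 16% is already half the annual figure, so the one-year label may be the error.
- That .9 power for physical IPA requires a fall to 3.3% whatever the method. That threshold belongs to one test with one outcome.

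The risk of misreading a null physical result is a possibility, not a demonstrated harm. The plan reports the prior null openly.

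**Conclusion.** The concern holds as a failure of support, not as proof of low power. The stated reason for ignoring dyadic correlation does not fit a total of 280, .38 has no level, the period of the 26% is inconsistent, and d changes from incidence to frequency.

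For psychological IPA, > .9 is plausible if r = .70 holds and baseline is used. For physical IPA, the approximations run from .40 to .87 with one outcome and from .48 to .93 with three averaged, so a blanket > .9 is not justified. The prior physical estimates of .10 and .26, with a standard error near .30, do not exclude .5, but they do not show that it is conservative.

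It would be tempting to conclude that the trial is underpowered. The documents do not show that: the link, contrast, time points and working correlation of the GEESIZE run are not given, and applying 26% to couples is an assumption that a couple composite might exceed.

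**What to change.** In (g) Power Analysis:

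- Fix one analysis unit: 140 couple composites, or 280 perpetrator scores with a stated dyadic ICC.
- State the group ICC used, and say what .38 is or delete it.
- Correct the period that the 26% covers.
- State the scale of d and whether it refers to incidence or frequency.
- Rerun for the intervention-by-time contrast.
- Replace the blanket > .9 with separate figures for psychological IPA (with d) and physical IPA (with the two proportions and the period). If physical IPA falls below .9, say so plainly.

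The cost is one rerun and one rewritten paragraph. No added enrolment is proposed. The only downside is a less favourable stated power for physical IPA; psychological IPA may well keep > .9.
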